2. STUDY OBJECTIVES

Part 1: To identify the highest tolerated dose of Imatinib (in the range of 100mg and 400mg once daily for 4 weeks) in patients with PAH.

Part 2: To assess the efficacy of Imatinib administered at the highest tolerated dose (once daily for 24 weeks) on PVR in PAH patients according to genes that regulate PDGF activity.

3. STUDY OUTCOME MEASURES

3.1 Primary outcome measures:

- Part 1: Discontinuation of the drug for more than 5 consecutive days due to Grade 2 or above Adverse Events defined by the National Cancer Institute (NCI) Common Terminology Criteria for Adverse Events (version .5.0, 2017), adapted for this study - see Appendix 2.
- Part 2: The primary efficacy endpoint is a binary variable. For patients with a baseline PVR >1000 dynes·s·cm⁻⁵, success is defined by an absolute reduction in PVR of ≥300 dynes·s·cm⁻⁵ at 24 weeks. For patients with a baseline PVR ≤1000 dynes·s·cm⁻⁵, success is a 30% reduction in PVR at 24 weeks.

3.2 Secondary outcome measures:

- Change in PVR from baseline according to genes that regulate PDGF activity.
- Change in 6MWD at 24 weeks.
- Change in right ventricular ejection fraction (RVEF) values, measured in echocardiogram (at screening assessment and at 24 weeks).
- Change in plasma brain natriuretic peptide (proNT-BNP) levels from baseline at 24 weeks.

• Change in Quality of Life (QoL) scores (23) from baseline at 24 weeks.

3.3 Exploratory outcome measures:

• Change in plasma proteome from baseline at 24 weeks.

4. INVESTIGATIONAL PLAN

4.1 Overall study design and plan

Patients will be invited to participate by their local designated pulmonary hypertension hospital. Suitable patients will be treated with Imatinib once daily for up to 24 weeks. The study is in two parts. The screening and consenting procedures are the same for Parts 1 and 2.

Part 1 will recruit 6 to 13 patients to identify the highest tolerated dose of Imatinib within the 100mg to 400mg per day range. This dose will then be used in Part 2 in a separate group of patients to assess efficacy according to the genes that relate to PDGF activity. It is necessary to find a single dose to maximise the opportunity to assess variation in response by genotype (i.e. reduce the influence of variation in exposure). It is necessary to find the highest tolerated dose to maximise the opportunity to capture a clinical response (i.e. reduce the chance of missing an effect). A starting dose of 100mg is based on experience from compassionate use; some patients, such as the case report above, have reported benefit from this dose. Doses of 200mg to 400mg daily were investigated in IMPRES (10) and many patients ended up on 200mg daily in the extension study. Our prior model of toxicity -see Section 10; skeleton- predicts that 200mg daily is likely to be the highest tolerated dose in PAH, and Part 1 is designed to explore this. A lower dose will be investigated in the efficacy phase if better tolerated.

Some patients with PAH attending the specialist clinics have both an implanted cardiopulmonary monitor and an activity monitor that permits remote sensing and a remote system for provision of daily blood pressure, oxygen saturations and body weight. These offer a particular advantage in a time of Covid-19, minimising contact with the hospital. The monitoring also offers greater oversight of the patient and closer safety monitoring. Remotely acquired patient data are reviewed twice a week via a central clinical team based in Sheffield. Many of these patients would be suitable for Part 1 of this study where the emphasis is on identifying a tolerated dose. These patients would not require a baseline RHC, as key data would be retrieved from the implanted monitor. Relevant data will be sent as de-identifiable information to the recruiting site for upload onto the study database (eCRF). Continuous monitoring data can be sent to Imperial College London (upon request) as pseudonymised (coded) data for consideration of the Trial Steering and Data Monitoring Committees, if there are any concerns regarding patients' safety. Follow-up would be scheduled by telephone or video conferencing with hospital visits being optional. Participants who consent to take part but do not have an implanted cardiac monitor will attend the hospital for a baseline RHC and then again at the end of Week 4 after starting Imatinib to assess tolerability, with telephone or video conference assessments at the end of Weeks 1, 2 and 3.

We will explore 4 doses between 100mg and 400mg of Imatinib (100mg, 200mg, 300mg and 400mg), the maximum dose escalation between patients is limited to 100mg to protect against rapid escalation to an intolerable dose. The first patient will receive Imatinib 100mg (x1) once daily. Subsequent patients will enter the trial at no less than 4 week intervals. The second patient will receive a dose of Imatinib based on the experience of the previous patient(s) at 4 weeks; if 100mg is tolerated, the second patient will receive 200mg. The third patient will receive a dose of Imatinib based on the experience of the previous patients at 4 weeks, using a statistical model to identify the most likely highest tolerated dose. This will be between 100mg and 300mg daily. The statistical model will be used to choose the dose for the fourth patient up to a maximum of 400mg daily.

By definition, the highest tolerated dose is reached in this trial when there is a 20% probability that a patient will not be able to continue the drug for 5 consecutive days. All patients who are tolerating Imatinib will be asked to continue on their assigned dose to the end of week 24 and their clinical

response will be measured by the change in PVR (measured through a follow-up RHC). Dose adjustments within the range 100mg to 400mg daily are permitted at the discretion of the responsible physician according to clinical need but if a patient is unable to tolerate 100mg daily, they are withdrawn from the study.

The objective of Part 2 is to define the clinical response to Imatinib after 24 weeks treatment with the highest tolerated dose by measuring the change in PVR through a follow-up RHC. Some patients from Part 1 will have continued on the highest tolerated dose to 24 weeks and so be evaluable for additional efficacy at this dose. Part 2 will continue recruitment of additional patients to a total of 34 evaluable patients; all patients in Part 2 will receive the highest tolerated dose (defined in Part 1) for 24 weeks. Patients will be monitored for safety at the end of Weeks 4, 8, 12 and 24, with telephone assessments at the end of Weeks 16, 20, and 28. If a patient becomes intolerant of Imatinib, they will be allowed to continue with a reduced dose or alterative treatment as guided by their NHS specialist physician, but they will be withdrawn from the study. Beyond that point, we will not be collecting new data from those patients. The clinical response of all patients who complete 24 weeks on the highest tolerated dose of Imatinib will be measured by change in PVR from baseline at Week 24. The primary efficacy endpoint is a binary variable: for patients with a baseline PVR >1000 dynes·s·cm⁻⁵, success is defined by an absolute reduction in PVR of ≥300 dynes·s·cm⁻⁵at 24 weeks; for patients with a baseline PVR ≤1000 dynes·s·cm⁻⁵, success is a 30% reduction in PVR at 24 weeks.

An interim analysis is planned after 13 patients have completed the 24 week treatment on the highest tolerated dose. If there are 1 or no responses in these patients, the study will be stopped. Otherwise, additional patients will be recruited for a total of 34 evaluable patients. The null hypothesis will be rejected if 7 or more responses are observed in the 34 patient cohort. Blood levels of Imatinib will be measured in each patient at baseline and at the end of Weeks 4 and 24. A trough level (noting the time for last dose) will be measured at the assessment on Week 4 and that on Week 24. Dose-limiting toxicity is defined as discontinuation of treatment for more than 5 consecutive days due to Grade 2 or above Adverse Events defined by the NCI Common Terminology Criteria for Adverse Events (version 5.0, 2017), adapted for this study - see Appendix 2. The criteria have been adapted by removing reference to pulmonary hypertension as an adverse event (since this is the indication for this study).

The most common recognised side effects of Imatinib include:

- Muscle cramps
- Joint pains
- Nausea and vomiting
- Swelling of the ankles and face
- Skin rash
- Loose stools
- Unusual bleeding or bruising
- Fatigue

Leg oedema and weight gain can also indicate deterioration in PAH due to right heart failure, rather than Imatinib toxicity. At the discretion of the study physician, a trial of increased dose of diuretics is permitted to help reduce the oedema and weight gain. If the oedema and weight gain are judged to be due to Imatinib toxicity, the dose of Imatinib may be reduced or the drug stopped and the patient is managed according to best clinical practice.

If a patient is unable to continue with the prescribed dose of Imatinib to 24 weeks, they will be withdrawn from the study. These patients may continue with a lower dose of Imatinib or discontinue the drug under the guidance of their local NHS specialist physician.

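### The Part 1 dose-adjustment sentence in Section 4.1 allows an increase within a patient, at any time, above any dose yet cleared by the model and the committees

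*Protocol*

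**What the plan says.** Section 4.1 opens the four Part 1 doses in steps. Patient 1 receives 100 mg. Patient 2 receives 200 mg if 100 mg was tolerated. Patient 3 receives between 100 and 300 mg. For the next patient, "The statistical model will be used to choose the dose for the fourth patient up to a maximum of 400mg daily". The stated reason for the step size is that "the maximum dose escalation between patients is limited to 100mg to protect against rapid escalation to an intolerable dose". On timing, "Subsequent patients will enter the trial at no less than 4 week intervals".

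Two further controls stand elsewhere. Section 4.2 describes escalation from patient to patient, guided by the model and a Data Monitoring Committee, and gives the decision to escalate to independent committees. Section 10 repeats the 100 mg limit relative to the previous patient, again as a rule on escalation between patients.

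For patients already on treatment in Part 1, Section 4.1 first sets a default: "All patients who are tolerating Imatinib will be asked to continue on their assigned dose to the end of week 24". It then adds that "Dose adjustments within the range 100mg to 400mg daily are permitted at the discretion of the responsible physician according to clinical need", followed by a floor: "if a patient is unable to tolerate 100mg daily, they are withdrawn from the study". Later in Section 4.1, for oedema and weight gain judged to be toxicity, "the dose of Imatinib may be reduced or the drug stopped". The section ends with a paragraph, not limited to either part, that withdraws any patient who cannot stay on the prescribed dose to 24 weeks.

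**The concern.** The adjustment sentence sets a floor but no ceiling below the top of the trial's dose range. It speaks of adjustments, not reductions, and its trigger is clinical need, not intolerance. A patient whose disease worsens on 100 mg would meet that trigger as readily as one with side effects. Nothing ties an increase to the 4-week assessment or to doses already opened.

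Two things are at stake:

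- **Safety.** The stepwise opening keeps patients away from doses for which the trial has no tolerability experience yet. An increase at one physician's discretion can bypass it.
- **Dose attribution.** The 4-week tolerability outcome of each patient feeds the model and sets the next patient's dose (Sections 4.1 and 10). If a dose is raised within those 4 weeks, the outcome no longer describes the assigned dose. With only 6 to 13 patients in Part 1, each outcome carries weight.

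**Working it through.** The protocol states no figure on this point, so there is none to reproduce. The check has two parts: what each rule governs, and how far the literal permission reaches.

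**1. What each rule governs**

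| Rule | Place | Governs |
|---|---|---|
| At most +100 mg, to avoid rapid escalation | Section 4.1 | Dose of the next patient |
| Escalation decided by independent committees | Section 4.2 | Described as escalation from patient to patient |
| At most 100 mg above the previous patient | Section 10, Part 1 | Introduced as escalation between patients |
| Adjustment anywhere in 100 to 400 mg | Section 4.1 | A patient already on treatment |
| Reduce or stop | Section 4.1 | Oedema and weight gain judged to be toxicity |

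The first three rules do not expressly reach a change within a patient. The fourth does, and has no cap below 400 mg. The fifth covers one clinical situation and does not narrow the fourth.

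**2. Size of the literal excess at entry**

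Inputs: start at 100 mg, steps of at most 100 mg, top dose 400 mg (all Section 4.1). I take the cleared dose to be the highest dose that the model and the committees have opened at that time.

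Highest dose that can be open to patient k = min(100 × k, 400) mg. Smallest excess = 400 − that value. Largest excess = 400 − 100 = 300 mg, if nothing above 100 mg has been opened.

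| Patient | Highest possible open dose | Smallest excess | Largest excess |
|---|---|---|---|
| 1 | 100 mg | 400 − 100 = 300 mg | 300 mg |
| 2 | 200 mg | 400 − 200 = 200 mg | 300 mg |
| 3 | 300 mg | 400 − 300 = 100 mg | 300 mg |
| 4 onward | 400 mg | 400 − 400 = 0 mg | 300 mg |

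The zero in the last row holds only if every step was opened at the first opportunity. Section 4.1 expects 200 mg to be the highest tolerated dose. If the model settles there, the excess for later patients is 400 − 200 = 200 mg.

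**3. How long the gap lasts for the first patients**

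At the fastest permitted entry, 4 weeks apart, patients 1 to 4 start at weeks 0, 4, 8 and 12. So 400 mg cannot be opened before week 12. It is still closed for at least:

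- patient 1: 12 − 0 = 12 of 24 treatment weeks (50%)
- patient 2: 12 − 4 = 8 of 24 weeks (33%)
- patient 3: 12 − 8 = 4 of 24 weeks (17%)

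Slower entry or slower escalation lengthens these periods.

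**The case against.** The strongest reply is that the rules address different subjects. The caps and the committees' decision concern the dose assigned to the next patient; the adjustment sentence concerns patients already treated. That is correct, and it disposes of a stronger reading that a reader might infer, namely that the protocol contradicts itself outright. It does not. But the same fact means that nothing else in the text clearly limits an increase within a patient.

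The second reply is context. Patients who tolerate the drug are asked to stay on their assigned dose, the sentence ends with the 100 mg floor, and the range may merely restate the trial's dose range, since some patients may be assigned 400 mg. The sentence also follows the request to continue to week 24, so an increase in the first 4 weeks is hypothetical. This makes reductions the likely main intent. It would be wrong to infer that the sponsor means to let physicians escalate. The wording still permits it.

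A third reply is that Section 10 limits what each patient receives, which would leave only patient 1 exposed. That fails on its own terms: once patient 1 has been raised to 400 mg, a limit of 100 mg above the previous patient no longer holds patient 2 to 200 mg.

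Nor does the extension phase supply a general ceiling. Its limit, at or below the highest tolerated dose, applies to patients 14 to 17 only. For the dose-finding patients, Section 10 recommends the dose closest to 20% toxicity, which is a target.

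Two points for the other side stand in full. Doses of 200 to 400 mg were already studied in the earlier Phase III trial. And Section 11.3 leaves the clinician free to depart from protocol treatment in the participant's interest, so no wording in Section 4.1 removes discretion entirely.

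**Conclusion.** The point holds as an uncapped permission to raise the dose within a patient, one that undercuts the stated purpose of the stepwise escalation. Read literally, the excess over the cleared dose is up to 300 mg for patient 1, at least 200 mg and 100 mg at entry for patients 2 and 3, and above zero for later patients for as long as the model keeps the dose below 400 mg.

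These figures bound the wording. A reader might take them as the overdose to be expected, but the documents do not support that: staying on the assigned dose is the default, and reductions are the likely intent. The figures assume that a dose counts as cleared once the model and the committees have opened it, and that the between-patient caps do not reach changes within a patient. Expected harm is limited. The point is worth acting on because the sentence is a dosing rule in the protocol itself and is easily repaired.

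**What to change.** In Section 4.1, amend the Part 1 text to state that:

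1. Discretionary adjustments are reductions, with return to the assigned dose allowed.
2. An increase above the assigned dose may occur only after the patient's own 4-week tolerability assessment, and only to a dose already cleared by the model and the committees.
3. The closing paragraph of Section 4.1, which withdraws patients unable to continue the prescribed dose, does not override the reductions permitted in Part 1.

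The cost is a short text change in one section and slightly less freedom for the treating physician. Sample size, schedule and model are unaffected.

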4.3.3 Subject completion

Subjects will be considered complete for the purpose of this study once they have completed all procedures of the follow-up telephone assessment or unscheduled visit at the end of Week 28 (or 4 Weeks after early termination). The end of the clinical trial is defined as the last assessment of the last subject undergoing the trial.

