4.3.4 Discontinuation criteria

It is possible that the Sponsor or the Competent Authorities request termination of the study if there are concerns about conduct or safety, or due to a change in the opinion of the Ethics Committee.

When the Sponsor is aware of information on matters concerning the quality, efficacy, and safety of the study drug, as well as other important information that may affect proper conduct of the clinical study, the Sponsor may discontinue the clinical study and send a written notice of the discontinuation along with the reasons to the Investigators. Patients will be informed that they have the right to withdraw from the study at any time for any reason, without prejudice to their medical care. The site Investigator/Chief Investigator can discontinue subjects from the study for any of the following reasons:

- 1. Occurrence of an unacceptable Adverse Event due to Grade 2 or above defined by the NCI Common Terminology Criteria for Adverse Events (version 5.0, 2017), adapted for this study -see Appendix 2.
- 2. Subject request
- 3. Subject is lost to follow-up
- 4. Administrative reasons
- **5.** Development of an intercurrent illness, condition, or procedural complication, which would interfere with the subject's continued participation
- 6. Patient becomes pregnant

The site Investigator/Chief Investigator also reserves the right to discontinue subjects in the interest of subject safety and welfare. Investigators must contact all participants and the hospital pharmacy (where applicable) to notify them of the termination of the study. In cases of an early termination (discontinuation), a follow-up telephone assessment will be performed 4 weeks ± 3 days -see Appendix 1.

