6.11 End of treatment assessment (Week 24 ± 3 days)

The patient will be invited to attend their local hospital at the end of Week 24 (or earlier if early termination of imatinib) in order to undergo the following procedures (in the case of patients with an implanted CardioMEMSTM device, a home assessment will be offered):

- Physical examination
- Concomitant medications
- Document AEs
- Vital signs: (i) Resting supine BP, (ii) pulse measurement, (iii) temperature, (iv) pulse oximetry (incl. respiratory rate), and (v) weight
- ECG
- WHO Functional Class
- 6MWT and Borg dyspnoea index
- Right heart catheterisation*(unless the patient has an implanted CardioMEMS™ device)
- Echocardiogram
- QoL questionnaire
- Blood samples for haematology and clinical chemistry, and serum pregnancy test whereas indicated (for women of childbearing potential)
- Blood sample for Imatinib levels
- · Research blood sampling

Review of the diary, Imatinib collection and reconciliation
 *can be performed on a separate day ± 3 days apart from the original visit date, as needed.

6.12 Follow-up telephone assessment (Week 28, or 4 weeks after early termination ± 3 days)

At the end of the study, clinical follow-up will continue via the local NHS-designated pulmonary hypertension clinics. The patients that have completed the 24-week treatment period on Imatinib may continue with the study drug under the supervision of their local NHS specialist physician. Those who discontinue Imatinib will be reviewed by their local physician for alternative treatment. In all cases, patients will receive a telephone call from the study physician/clinical study team once they have been off study drug for 4 weeks (±3 days) to check concomitant medications, and for the occurrence of AEs. Patients will be also asked to weigh themselves and report their weight and ankle swelling. For women of childbearing potential: A urine pregnancy test will be performed at home. A telephone call will be performed within 72 hours of the urine test date to enquire about the results.

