11.3 Informed consent

Consent to enter the study must be sought from each participant only after a full explanation has been given, an information leaflet offered and time allowed for consideration. Signed participant consent should be obtained. The right of the participant to refuse to participate without giving reasons must be respected. After the participant has entered the trial the clinician remains free to give alternative treatment to that specified in the protocol at any stage if he/she feels it is in the participant's best interest, but the reasons for doing so should be recorded. In these cases the participants remain within the study for the purposes of follow-up and data analysis. All participants are free to withdraw at any time from the protocol treatment without giving reasons and without prejudicing further treatment.

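### Section 4.1 stops all data collection once an intolerant Part 2 patient is withdrawn, against the 4-week safety call in 4.3.3, 4.3.4 and 6.12 and the continued follow-up in 11.3

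*Protocol*

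**What the plan says.** The Part 2 paragraph of Protocol Section 4.1 allows an intolerant patient to move to a reduced dose or another treatment under the NHS physician, but withdraws that patient from the study. It continues: "Beyond that point, we will not be collecting new data from those patients". A later paragraph of 4.1 repeats the withdrawal for anyone who cannot stay on the prescribed dose to 24 weeks, and adds: "These patients may continue with a lower dose of Imatinib or discontinue the drug under the guidance of their local NHS specialist physician".

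Other sections describe what happens after an early exit:

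- Section 4.3.3 treats a subject as complete only after the "follow-up telephone assessment or unscheduled visit at the end of Week 28 (or 4 Weeks after early termination").
- Section 4.3.4 says: "In cases of an early termination (discontinuation), a follow-up telephone assessment will be performed 4 weeks ± 3 days".
- Section 6.12 says: "In all cases, patients will receive a telephone call from the study physician/clinical study team once they have been off study drug". The off-drug interval that it sets is 4 weeks, give or take 3 days. The call covers concomitant medication and adverse events, and further: "Patients will be also asked to weigh themselves and report their weight and ankle swelling". Women of childbearing potential also do a home urine pregnancy test.
- Appendix 1 footnote g allows the call after early termination, on condition that the patient has been off study drug for 4 weeks.
- Section 11.3, on patients whose clinician gives a treatment other than the protocol's, says: "In these cases the participants remain within the study for the purposes of follow-up and data analysis".

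**The concern.** Two rules for the same patients cannot both be followed. A site that takes 4.1 as written makes no contact after withdrawal. A site that takes 4.3.3, 4.3.4 and 6.12 as written makes a safety call about four weeks later. No text ranks one above the other.

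The matter is safety-related because Section 1.1 names safety and tolerability as what has held back imatinib in PAH. The affected patients have already shown toxicity, and some stay exposed at a lower dose. Section 8.4 sets reporting procedures for the screening and treatment periods only. Once the exit visit is done, this call is the one remaining scheduled safety contact in Appendix 1. Chiefly at stake are adverse events that begin after withdrawal, together with the other items of the call.

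**Working it through.** The point is textual, so the check is whether the passages govern the same patients and the same data.

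1. **Same patients?** Yes. Section 4.3.4 lists reasons for taking subjects out of the study, and the first is an unacceptable adverse event of Grade 2 or above. The call is required for these early terminations. One cannot rescue 4.1 by saying that 4.3.4 concerns only patients who stop the drug but stay in the study.

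2. **Is the call new data?** Yes. It collects adverse events, concomitant medication, weight, ankle swelling and, where relevant, a pregnancy test result, all after withdrawal. Sections 4.3.3 and 4.3.4 require the assessment. Section 6.12 supplies its content.

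3. **Does 11.3 conflict too?** Yes, for patients moved to alternative treatment: 4.1 ends their data collection and 11.3 continues it.

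4. **Does the early end-of-treatment assessment conflict (6.11, 7.7, 7.8)?** Not necessarily. It can be read as the exit visit at withdrawal, which is compatible with 4.1, so it is not counted here.

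5. **When is the call due?**
 - Under 4.3.4: 4 weeks ± 3 days after early termination, that is 28 − 3 = day 25 to 28 + 3 = day 31.
 - Under the body of 6.12 and footnote g: the same interval, counted from stopping study drug.
 - If the patient stops imatinib at withdrawal, the two starting points coincide, and the conflict of 6.12 with 4.1 is direct.
 - If the patient is withdrawn on a reduced dose, the off-drug date may never occur and the trigger stays open. While such a patient is still taking imatinib, 6.12 and footnote g do not contradict 4.1. Sections 4.3.3 and 4.3.4 do, and so does 11.3 where it applies.
 - The heading of 6.12 itself counts from early termination, so heading and body disagree.

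6. **Do the design figures depend on this?** The Section 10 figures for Part 2 reproduce by exact binomial sums (13 then 21 patients; stop at 1 or fewer responses; reject at 7 or more of 34):
 - Early termination at a response rate of 0.10: P(X ≤ 1 | n = 13) = 0.6213.
 - Expected sample size: 13 + (1 − 0.6213) × 21 = 20.95, stated as 21.
 - Type I error: 0.0420. Power at 0.27: 0.8034.

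 All four match the protocol. The telephone call enters none of them.

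**The case against.** The strongest reply is that 4.1 is a design overview and the operative sections agree with each other. Sections 4.3.3, 4.3.4 and 6.12 and the schedule all provide for the call, and 6.12 says it applies in all cases. The 4.1 sentence stands just before the text on measuring clinical response, so it could be meant for efficacy data only. Even if a site followed 4.1, the event that led to withdrawal is already recorded. Serious events in the treatment period are reported within 24 hours (8.4.2.2), events still ongoing at the end of the study are followed to resolution (8.7), and the NHS clinics continue care (6.12).

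Much of this stands. The intent to make the call is fairly clear, and the loss is conditional and small. But the limit to efficacy data is an inference that 4.1 does not state. Section 4.1 is also the text that speaks directly to intolerant Part 2 patients, so a site could reasonably follow it. Nor does agreement among the other sections help a patient on a reduced dose, for whom the 6.12 trigger may not fire.

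A reader might go further and infer that completers will miss their call, because "patients that have completed the 24-week treatment period on Imatinib may continue with the study drug". The documents do not support that: the 6.12 heading, the Appendix 1 column and 4.1 all place this contact at Week 28. For completers only the wording in the body of 6.12 is loose.

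**Conclusion.** The contradiction is real and lies in the current text. Section 4.1 rules out data that 4.3.3, 4.3.4 and 6.12 require and that 11.3 presupposes. Separately, the off-drug timing in 6.12 and footnote g may leave patients withdrawn on a reduced dose without the call that 4.3.3 and 4.3.4 require.

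The size is one telephone contact, due on day 25 to 31, for each withdrawn patient at a site that follows 4.1 or waits for the off-drug trigger. Sites that follow 4.3.3 and 4.3.4 lose nothing. The protocol gives no withdrawal rate for Part 2. The 20% target toxicity of Part 1 is not one, and it would not count missed calls either, so no number of affected patients is offered.

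Two stronger readings should be resisted. One is that safety data on withdrawn patients are lost altogether; the provisions for recording, reporting and following events show otherwise. The other is that the primary test is compromised by this inconsistency; no effect on an endpoint, a dose decision or an error rate has been shown. Priority is minor to moderate.

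**What to change.** In 4.1, replace the withdrawal and no-new-data wording with: *withdrawn from study treatment; the early end-of-treatment assessment (6.11), the 4-week telephone assessment (4.3.4, 6.12) and follow-up of adverse events are still completed, including for patients who continue a reduced dose, unless consent to data collection is withdrawn.*

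In 6.12 and Appendix 1 footnote g, time the call from the date of withdrawal from study treatment, and at Week 28 for completers, whether or not the patient is still taking imatinib.

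Do not add a statement that efficacy assessments stop at withdrawal. That would leave the conflict with 11.3 open and would write a no-follow-up rule into a protocol whose primary analysis is intention-to-treat (Section 10).

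The cost is a short amendment and one telephone call for each patient withdrawn on a reduced dose. The Week 28 call for completers is already scheduled. This costing takes the early assessment in 6.11 as already due at withdrawal. Section 6.11 words its trigger as early termination of imatinib, so a sponsor who reads it as covering only patients who stop the drug should decide openly whether reduced-dose patients also have that visit. It includes a catheterisation of about 7 mSv (7.10) unless the patient has an implanted monitor.
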